Respirometry of platelets, peripheral blood mononuclear cells, and neutrophils on admission, 3 hours, 6 hours, 12 hours, 24 hours, 48 hours, and 5 days post admission; Development of multiorgan failure within 30 days of admission; Level of free serum free nucleic acids; Expression of pro and anti-inflammatory proteins and genes and genetic variants in serum, platelets, and white blood cells.

Background

Traumatic injury results in 5-6 million deaths per year worldwide with \$518 billion global cost with about half of trauma deaths due to acute blood loss. Acute blood loss and standard resuscitation with crystalloids and stored blood products causes hypothermia, acidosis, tissue hypoxia, hypotension, inflammation, the activation and consumption of coagulation factors including platelets, the release of free nucleic acids, the development of mitochondrial dysfunction and eventually organ failure. Importantly, about a quarter of trauma patients display a coagulopathy, (trauma induced coagulopathy, TIC) which greatly increases the risk of death and/or the development of multiorgan failure. We currently, however, cannot predict who will develop TIC or its associated complications. In fact, two patients who have the same clinical presentation may have very different outcomes. Developing a multi scale computational model and ex-vivo point of care assays would allow us to efficiently identify and effectively treat at risk patients and potentially improve outcomes.

Study Design

Phase*

Not applicable

Design

Prospective, observational, convenience sampling of trauma patients 18 yrs old or older who present to the trauma bay will be included. Minimally injured patients will be compared to those with a systolic blood pressure of 90 mmHg or less, the need for blood product transfusion within 1 hour of admission, and/or an ISS of greater than or equal to 15. Demographic data including past medical/medication history as well as clinical data including continuous vital signs (when available) will be recorded. Blood samples (approximately 15 ml) and urine samples (approximately 10 ml) will be taken on admission, 3hr, 6hrs, 12hrs, 24 hrs, 48 hrs, and 5 days post admission. Residual blood samples (which would otherwise be discarded) will be obtained from the PPMC clinical laboratory on 0 and 2 days post admission. Blood samples may be analyzed for coagulation parameters included ex vivo microfluidic

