In addition to the PI's ([name] and [name]), this research will be conducted by the Penn Acute Research Collaboration (PARC) research coordinators and assistants. PARC provides 24 hour translational research services to the Penn Presbyterian community. All PARC research staff are CITI trained and will be familiar with the study protocol and execution prior to its initiation. The PI is a qualified trauma surgeon with clinical trial experience and training. The PARC research coordinators have clinical research experience and will directly oversee the training of research assistants in order to coordinate the study and ensure compliance. After each enrollment, the study coordinator will evaluate for study compliance. The entire research staff will conduct monthly meetings and the PI and research coordinator will meet at least every 2 weeks. All patients, including enrolled subjects, will be admitted to the trauma and surgical critical care service. They will be managed according to generally accepted medical standards for traumatic injury, which includes surgical interventions, damage control maneuvers, and sub-specialty consultation as needed and at the discretion of the treating trauma surgeon/surgical intensivist. Blood and urine samples will be processed and analyzed in the trauma at PPMC as well as at the PARC facility on 3 Mutch, PPMC. Blood and urine samples and case report forms will be stored at the PARC facility on 3 Mutch, PPMC.

Characteristics of the Study Population

Target population

trauma patients 18 years or older who present to the trauma bay

Subjects enrolled by Penn Researchers

300

Subjects enrolled by Collaborating Researchers

0

Accrual

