Patients who develop coagulopathy, altered cellular respiration, or multi-organ failure will be compared using T-tests or Mann-Whitney tests for continuous variables and Chi-squared or Fischers exact tests for dichotomous variables. Spearman's rank correlation will be used to assess associations between continuous variables. Logistic regression analysis will be used to identify risk factors for the development of trauma induced coagulopathy or multiorgan failure.. Receiver operating characteristic curves will be used to assess accuracy of microfluidic measurements compared to standard measures of coagulation . Continuous deidentified data including vital signs, laboratory values, and medications will be shared with collaborators at Princeton University in order to create a mathematical model. The computational whole-patient systems model is a multiscale, multi-compartment model whose state-space is defined by a very large and heterogeneous set of variables as well as a large number of input parameters. It is straightforward to make direct contact with the clinical trauma blood profiles because the measured variables in these profiles are also included in the model state space. This comparison first will be used to establish the validity of the model. Here, the model will simply be integrated in time for various initial trauma conditions in an attempt to determine whether the model can be predictive. In particular, we will determine whether it is possible to reproduce the variation between the various time states at admission,3, 6, 12, 24, 48 hours and 5 days post admission. A more challenging data mining application is to discover new variables that are more predictive of clinical outcomes than those employed in current clinical protocols. The workhorse data mining technique we plan to explore, extend, and use to establish links between our multiscale model and clinical data is known as Diffusion Maps. This is a framework based upon diffusion processes for finding meaningful geometric descriptions of data sets, even when the underlying geometry of the data is complex, nonlinear and corrupted by noise. The method is based on the construction of a Markov transition probability matrix corresponding to a random walk on a graph whose vertices are the data points with transition probabilities being the local similarities between pairs of data points. The framework relates the spectral properties of Markov processes to their geometric counterparts and it unifies ideas arising in a variety of contexts such as nonlinear dimensionality reduction methods, machine learning, and harmonic analysis. The first few eigenvectors of the sparse Markov matrix are then used to generate a new set of intelligent coordinates that embody the intrinsic geometry of the data set. These are the diffusion map coordinates. Most importantly, these eigenvectors integrate the local similarities into a globally efficient low-dimensional representation of the complex geometric structure. The usage of eigenvectors of similarity matrices for dimensionality reduction is not new. In fact, the classical method of principal component analysis (PCA) computes principal components as eigenvectors of the covariance matrix of the data set and find a low dimensional representation of the data by projecting it onto the subspace spanned by the first few principal components that capture the most variability (or energy) of the data. Diffusion Maps is a successful generalization of PCA to complex nonlinear data sets whose structure is unknown in advance: unlike PCA, the diffusion map coordinates are nonlinear projections of the data; moreover, the nonlinear embedding is based only upon local similarities of neighboring data points. Diffusion Maps first will be used on the multiscale simulation data sets. This will establish macroscopic observables that define the trajectory of the overall patient-scale model. This is crucial because it is much simpler to establish a connection to patient outcome when only a few variables are being tracked (instead of the large variable space that defines the full multiscale model). However, these variables are generally not obviously connected to clinical variables and we will use the simulation data to establish relationships between the Diffusion Maps variables and actual measureable quantities. The result of this work will be to isolate variables that are highly predictive of patient outcome and allow assessment of different interventions.

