Trauma remains the leading cause of death for those under the age of 40 in the United States, with a large percentage of patients dying from hemorrhagic shock within the initial post-injury hours. Potential therapeutic interventions will have the most impact if we can identify which patients are at risk for developing trauma induced coagulopathy, exuberant inflammation, and multi-organ failure. In order to develop a robust model, data and biologic samples will need to be collected BEFORE interventions in order to determine which interventions either positively or negatively influence outcomes. Given the unpredictability and emergent nature of trauma, potentially eligible patients cannot be identified prior to their arrival to the trauma bay. Moreover, patients who are severely injured and/or hemodynamically unstable are unable to consent for themselves. Frequently, these patients are rapidly intubated, aggressively resuscitated with blood products and brought to the operating room or IR suite for hemorrhage control within minutes of initial arrival. In general, the resuscitative effort is well on the way by the time the patient's family is located - a process that typically takes hours to days.

Additional Information to Subjects

Contact information from the patient and/or the surrogate will be kept in a separate file that is not associated with any HIPPA or study data. Participants will have the option of receiving a copy of the study results or manuscript at the conclusion of the study either by email or standard post.

Written Statement of Research*

No

If no written statement will be provided, please provide justification

The following documents are currently attached to this item:

There are no documents attached for this item.

Risk / Benefit**Potential Study Risks**

This study has minimal risk. Seven blood and urine samples with a maximum cumulative total volume of 105 ml and 70 ml, respectively, over 5 days is well tolerated. Every attempt to will be made to collect research samples during routine clinical phlebotomy or from existing lines. Blood samples will be collected only by nursing/medical/phlebotomy staff in order to minimize the minimal risk of pain and infection associated with routine phlebotomy.

Potential Study Benefits

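### Do the protocol's remarks about judging interventions call for a causal analysis, or for a rule on admission samples drawn after treatment?

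*Combined protocol and SAP*

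**What the plan says.** Interventions are mentioned in two places.

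- **Waiver Essential to Research**, which justifies drawing blood before consent: "data and biologic samples will need to be collected BEFORE interventions in order to determine which interventions either positively or negatively influence outcomes".
- **Analysis Plan**, last sentence: the modelling is expected to "isolate variables that are highly predictive of patient outcome and allow assessment of different interventions".

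The **Overall objectives** are a prediction algorithm for trauma induced coagulopathy, validation of microfluidic models, and assays to predict inflammation and organ failure. The primary outcome is coagulation parameters from admission to day 5. No objective or outcome is a treatment effect.

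Care is given "at the discretion of the treating trauma surgeon/surgical intensivist" (**Resources necessary for human research protection**). One criterion for the more severely injured comparison group is "the need for blood product transfusion within 1 hour of admission" (**Design**).

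Under the **Analysis Plan**, patients who develop coagulopathy, altered respiration or organ failure "will be compared using T-tests or Mann-Whitney tests for continuous variables and Chi-squared or Fischers exact tests for dichotomous variables". The plan adds Spearman correlation, logistic regression for risk factors (no covariates named), ROC curves, a mechanistic model and Diffusion Maps.

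The first sample is planned with the routine admission bloods (**Accrual**, **Consent Process**, **Minimal Risk**). Sampling in unstable patients may be put off if it would interfere with care (**Procedures**, **Minimal Risk**), and the first sample is not exempted. Transfusions, crystalloid and medications are recorded (**Procedures**), and laboratory, medication and vital-sign files are downloaded from the electronic record (**Subject Confidentiality**).

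**The concern.** The waiver sentence is causal in wording: it speaks of interventions that help or harm. In an observational convenience sample treated by clinical judgement, sicker patients receive more treatment and do worse. The protocol ties the two together by using early transfusion as a marker of severity. An unadjusted comparison could then make a harmless treatment look harmful.

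The same sentence sets a condition, samples before treatment, that the deferral provision does not guarantee. The waiver section also says that severely injured or unstable patients are often resuscitated within minutes of arrival. Late first samples would therefore fall mainly among the sickest. The protocol does not say whether such a sample counts as an admission sample or as missing. A marker altered by treatment could then appear to predict outcome only because treated patients fare worse. Admission is both the first time point of the primary outcome and the first state the model has to reproduce.

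**Working it through.** The protocol gives no event rate, effect size or error rate on this point, so there is no figure to reproduce. Only n = 300 (**Subjects enrolled by Penn Researchers**) is documented. All other inputs below are assumptions.

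**1. Is there a treatment analysis that could be confounded?** The two-group tests split patients by outcome, and treatment is not named as a variable. The logistic regression is for risk factors and could include severity, though no covariates are listed. The closing remark in the Analysis Plan follows text in which "Diffusion Maps first will be used on the multiscale simulation data sets", so it can be read as interventions varied inside the model. That reading removes the issue only in part. "Continuous deidentified data including vital signs, laboratory values, and medications will be shared with collaborators" to build the model, and of the match with clinical profiles the plan says: "This comparison first will be used to establish the validity of the model". Still, no treatment contrast is stated.

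**2. What would happen if someone ran a crude treatment comparison?** Assume a treatment with no effect. Let half the patients be severe, treatment be given to 40% of severe and 10% of other patients, and outcome risk be 15% and 5%.

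- Treated share: 0.5×0.4 + 0.5×0.1 = 0.25, that is 75 of 300.
- Risk if treated: (0.5×0.4×0.15 + 0.5×0.1×0.05) / 0.25 = 0.13.
- Risk if untreated: (0.5×0.6×0.15 + 0.5×0.9×0.05) / 0.75 = 0.09.
- Crude odds ratio: (0.13/0.87) / (0.09/0.91) = 1.51, where the truth is 1.
- A two-sided 0.05 test of 75 against 225 patients rejects in about 19% of studies.

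Over the eight settings tried (severe share 50% or 70%; treatment 40% v 10% or 60% v 5%; risk 15% v 5% or 30% v 3%), the crude odds ratio runs from 1.31 to 3.13 and rejection from 12% to 94%. With severity as a continuous score, an odds ratio of 1.5 per SD for both treatment and outcome gives a crude odds ratio of about 1.17 and 6–10% rejection. An odds ratio of 2 gives 1.48–1.56 and 12–40%. The spread shows that the assumptions set the answer.

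**3. How much would late first samples matter for prediction?** Assume that 30% of patients are unstable, that a share q of them is drawn late, that the severity odds ratio is 2 or 3, that the outcome rate is 10% or 25%, and that treatment shifts an otherwise unrelated marker by d = 0.5 or 1 SD. If π₁ and π₀ are the late shares among patients with and without the outcome,

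AUC = 0.5 + (π₁ − π₀) × (Φ(d/√2) − 0.5).

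Take q = 50%, outcome rate 10%, odds ratio 3 and d = 1. About 9.8 of 30 cases and 45 − 9.8 = 35.2 of 270 non-cases are late, so π₁ − π₀ = 0.327 − 0.130 = 0.196. With Φ(0.707) − 0.5 = 0.260, AUC = 0.5 + 0.196×0.260 = 0.551. Simulated results over all settings:

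| Late among unstable | Late of 300 | Rejection (nominal 5%) | AUC (true 0.5) |
|---|---|---|---|
| 10% | 9 | 5.2–6.0% | 0.503–0.510 |
| 25% | about 22 | 5.2–10.8% | 0.508–0.525 |
| 50% | 45 | 6.3–25.8% | 0.517–0.551 |

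**4. Would a pre-treatment-only analysis settle it?** In the simulation it holds 4.8–5.4%, but that is built in: the marker is independent of severity and lateness is random among unstable patients. Coagulation markers that track severity need not behave this way. At 50% late the restriction also loses 8–10 of 30, or 18–22 of 75, outcome cases, and these are the sickest patients. It could only be supportive.

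**The case for a change.** The strongest case for a change is that the waiver sentence, unlike the closing remark in the Analysis Plan, has no in-model reading. It helps to justify delayed consent, and nothing in the analyses delivers what it promises. Regression is no cure for confounding by indication when no covariates are named. The protocol gives no way of knowing whether late first draws are rare or common. It does not say that draw times are kept, it does not mention recording of pre-arrival treatment, and it appears to leave transfers of up to 6 hours eligible. A time stamp and a sentence of caution would cost little.

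All of that is accurate, and two things stand: intervention findings from these patients would be hypothesis-generating at most, and the label for a late first sample is unwritten. Neither makes a planned analysis wrong. The sentence explains the timing of a blood draw; it does not commit the study to an estimate. A first draw taken with the clinical bloods needs no extra venipuncture, so it is the sample least likely to be put off. A study whose primary outcome is defined by hours since admission can hardly be run without logging collection times, although that is an inference. In-hospital treatment times should then be recoverable from the record. Pre-arrival care is less certain.

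**Conclusion.** No change to the plan is needed. The wording on interventions goes further than the analyses can support, but it lies outside the objectives and outcomes, and limiting it would alter no planned analysis. The unlabelled late first sample is a gap that analysts can fill sensibly: compare draw time with first recorded treatment, count the late samples, keep them all in the main analysis and report the number.

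On the assumptions above, the effect on prediction is negligible if about 9 of 300 first samples are late (rejection 5.2–6.0%). It becomes material only when lateness is common and treatment shifts the marker strongly (up to 10.8% at 25% late and 25.8% at 50% late). No section indicates that lateness is common. The conclusion rests on draw times being kept and on reports confining themselves to prediction and association. If a report were to claim that a treatment helped or harmed, the confounding shown in step 2 would apply in full.

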Clinical trials identifier: **NCT03128658**

Principal Investigator: **[name]**

Protocol Title: **Trauma Induced Coagulopathy and Inflammation**

Date: **August 2, 2018**

Protocol Description: **This is a prospective observational trial designed to evaluate the factors that contribute to the development of trauma induced coagulopathy, post injury inflammation and the development of organ dysfunction in adult trauma patients. Demographic data, physiologic data, blood samples and clinical variables will be collected over the 5 days following traumatic injury.**

Protocol

Abstract

While a number of factors are known to be associated with the development of trauma induced coagulopathy (TIC), inflammation, and multi-organ failure, we currently cannot predict which patients are at risk for developing these life-threatening conditions with any certainty. In this prospective observational study, we will investigate the many factors that contribute to the development of trauma induced coagulopathy, post injury inflammation and the development of organ dysfunction in order to develop a multi scale computational algorithm and ex vivo models capable of clinical prediction. Using a convenience sample technique, demographic data, physiologic data, fresh and residual blood samples, urine samples, and clinical variables will be collected over 5 days following traumatic injury. In addition to a computational model, ex vivo models using microfluidic devices and high resolution cellular respirometry, and nucleic acid analysis will be used to predict the development of TIC and multi-organ failure.

Objectives

Overall objectives

1) Develop a computational algorithm to predict the development of trauma induced coagulopathy (TIC) 2) Validate ex-vivo microfluidic TIC models 3) Develop ex-vivo assays to predict the development of trauma-induced inflammation and the development of multi-organ failure

Primary outcome variable(s)

Coagulation parameters including thromboelastography and microfluidic assessment on admission, 3 hours, 6 hours, 12 hours, 24 hours, 48 hours, and 5 days post admission.

Secondary outcome variable(s)

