This will be prospective observational study using convenience enrollment. Injured patients who present to the trauma bay will be evaluated by the on call trauma surgeon and as well as the PARC research assistant. If eligibility criteria are met, the research blood samples will be drawn at the same time as routine clinical samples. Depending on the research expertise available (e.g. microfluidic assessments or cellular respiration experiments), eligible patients may not have all the research variables investigated at each time point. Given that we will be recruiting a number of minimally injured patients, as well as injured patients with significant variability (eg severity of injury, age, gender, race, and past medical history), a large accrual number is required in order to develop a computational model that can accurately determine which factors predict the development of TIC, inflammation and

multiorgan failure.

Key inclusion criteria

In order to develop a robust predictive model, we will need to include a variety of injured patients ranging from minimally injured to severely injured. Inclusion criteria, therefore, will include any trauma alert activation. This highest level of activation is reserved for patients who meet either physiologic parameters (e.g. hypotension) or who have a mechanism of injury that would suggest significant injury (e.g. high speed motor vehicle crash). that being said roughly 30% of trauma alerts are not found to have significant injury. Only patient's whose age is equal to or greater than 18 years old will be included.

Key exclusion criteria

Transfer to trauma service of greater than 6 hours Known pregnancy - these patients are excluded because drawing multiple blood samples has an unknown risk to the fetus. Women of child bearing age, however, will be eligible. If they are found to be pregnant before enrollment, they will be excluded (eg. obvious gravid uterus, + fetus seen on trauma ultrasound, or + pregnancy test, which is routinely done on all female trauma patients) . If they are found to be pregnant after the initial blood draw, this sample will be processed, but no additional blood samples will be taken. The patient, or next of kin if appropriate, will be asked to consent for analysis of the processed sample and for continued clinical data collection.

Vulnerable

Populations

Children Form

Pregnant women (if the study procedures may affect the condition of the pregnant woman or fetus) Form

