48 hours and 5 days post admission. Blood and urine sample collection in unstable patients will be deferred or delayed if it is determined by the clinical team that taking the sample would interfere with clinical care. Smaller blood and urine volume samples maybe taken at each time point (eg 10 ml rather than 15 ml of blood) if research expertise is not available for sample analysis (e.g microfluidic or high resolution respirometry) at that time point. Residual plasma and whole blood samples will be collected from the PPMC clinical laboratory on day 0 and day 2 from trauma bay admission. Blood samples will be analyzed for coagulation and microfluidic flow parameters, proteins involved in inflammation and coagulation, mitochondrial function and respiration of white blood cells and platelets, DNA sequencing of specific genes involved in organ failure, and gene expression of proteins of interest. Residual samples will be further studied for protein biomarker measurements and DNA analyses. Urine samples will be analyzed for biomarkers of organ injury and dysfunction. Vital signs, number of blood transfusions, volume of crystalloid, administration of medications, and the values of routine laboratories will be monitored continuously for 24 hours, and then cumulatively for up to 5 days. This data will be collected by reviewing the electronic medical record via EPIC. Discrete data will be recorded on case report forms and then entered into REDCap - an institutionally approved and managed secure network that is also password protected. Continuous data will be deidentified and maintained on REDCap. The development of multiorgan failure will be monitored for up to 30 days post enrollment. If patients are discharged or die prior to completing the 5 days of blood samples, additional samples and/or clinic appointments for the purpose of research will not be obtained. After the last blood draw, we will be following the patient's outcome until discharge. This data is routinely extracted as part of the Pennsylvania Trauma Outcomes Study - a state trauma center requirement - and will not require additional contact with the patient. We will not personally follow up patients if they are discharged prior to 30 days.

The following documents are currently attached to this item:

There are no documents attached for this item.

Deception

Does your project use deception?

No

Analysis Plan

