This research involves minimal risk. The initial blood sample (15 ml) will be drawn at the time other blood samples are taken for standard clinical care. As such, it does not require an additional venipuncture. In total, 7 blood samples (a max of 15 ml per sample) will be taken over the course of 5 days. When research expertise is not available for specific assays (e.g microfluidics or respirometry) this blood volume will be decreased to 10 ml. Additionally, collections of research samples will be deferred or delayed if the clinical team feels that collection would interfere with the clinical care of an unstable patient. Moreover, a volume of 15 ml X 7 times over 5 days is the maximum amount of blood that will be collected. Many of these patients will be bleeding and will require a number of blood transfusions because of their injuries. Each blood transfusion is 300 ml. We do not feel that a maximum of 105 ml of blood over 5 days will pose a higher risk to our patients. Residual blood collection (which would otherwise be discarded) involves obtaining samples from the clinical lab on day 0 and day 2 and does not confer risk above loss of confidentiality. Lastly, sample collection of 10 ml of urine totaling 70 ml over 5 days imposes only minimal risk to the patient as it is a prospective collection via noninvasive means. The urine specimen will be obtained at the time staff is performing a clinical draw and collected directly from a Foley catheter or, if a catheter is not in place as part of standard care, from a spontaneous void.

Impact on Subject Rights and Welfare*

This study will attempt to protect the patient's rights by (1) informing and consenting the patient or surrogate prior to the initial blood draw and urine collection whenever practicable (2) informing and obtaining consent for continued participation when a surrogate is identified and (3) informing and consenting the patient when he/she regains capacity to make an informed choice. If consent is not obtained, the subject will be un-enrolled and the data and biological samples will be discarded.

Waiver Essential to Research*

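### Draws in unstable patients may be delayed without limit, but the primary outcome and the model check use nominal hours only, so late samples would meet the time-integrated model at the wrong time.

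*Combined protocol and SAP*

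**What the plan says.** **Outcome.** The primary outcome is "Coagulation parameters including thromboelastography and microfluidic assessment on admission, 3 hours, 6 hours, 12 hours, 24 hours, 48 hours, and 5 days post admission". No sampling window is given.

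**Collection.** The Procedures section schedules blood and urine at the same hours, then makes an exception: "Blood and urine sample collection in unstable patients will be deferred or delayed if it is determined by the clinical team" that sampling would interfere with care. The Minimal Risk section repeats it: "collections of research samples will be deferred or delayed if the clinical team feels that collection would interfere with the clinical care". Neither gives a maximum delay. Potential Study Risks adds a best-effort alignment: "Every attempt to will be made to collect research samples during routine clinical phlebotomy or from existing lines". For urine, Minimal Risk says: "The urine specimen will be obtained at the time staff is performing a clinical draw". The Accrual section says "the research blood samples will be drawn at the same time as routine clinical samples", which most naturally concerns the admission sample.

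**Analysis.** In the Analysis Plan, "the model will simply be integrated in time for various initial trauma conditions", and the test is whether it can "reproduce the variation between the various time states at admission,3, 6, 12, 24, 48 hours and 5 days post admission".

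**Recording.** Under Subject Confidentiality, clinical values go on the case report form at set time points, and continuous clinical files come from the electronic record. Neither statement mentions the clock time of a research draw. The coordinator's audit under Data and Safety Monitoring covers consent, data accuracy and storage, not draw timing.

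**The concern.** A model integrated in time predicts a value for a particular elapsed hour. If a sample labelled 3 hours was drawn at 5 hours, comparing it with the 3-hour prediction charges the model with two hours of biology that it was never asked to predict. A correct model can then appear to fail.

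The written delay rule applies to unstable patients, so the mismatch would fall on those whose early course the model most needs to describe. Their treatment also changes quickly: the waiver justification describes aggressive transfusion and transfer for haemorrhage control within minutes of arrival. Transfusions, fluids and medications are followed continuously for the first 24 hours. A late sample carrying a nominal label could therefore reflect treatment that the model places after that label.

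Draw times that nobody writes down may be impossible to recover later.

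**Working it through.** The documents give no figure for draw-time error, so there is nothing to reproduce. The check has three steps: compare the timing statements, express a delay on the scale of the sampling gaps, and test whether a group-level bias can be derived.

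**1. Timing statements side by side**

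| Question | What the documents give |
|---|---|
| Times that define the outcome and the model check | Nominal only |
| May draws depart from nominal times? | Yes: delay or deferral in unstable patients; best-effort alignment with clinical draws |
| Maximum delay or window | None stated |
| Actual research-draw time recorded | Not stated |
| Actual elapsed time used in the analysis | Not stated |
| How a late sample is labelled | Not stated |

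**2. Delay relative to the gaps**

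The gaps follow from the schedule: 3 − 0 = 3 h, 6 − 3 = 3 h, 12 − 6 = 6 h, 24 − 12 = 12 h. The displacement is delay ÷ gap; the delays are assumed.

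| Assumed delay | 0–3 h | 3–6 h | 6–12 h | 12–24 h |
|---|---|---|---|---|
| 1 h | 1/3 = 33% | 33% | 1/6 = 17% | 1/12 = 8% |
| 2 h | 2/3 = 67% | 67% | 2/6 = 33% | 2/12 = 17% |

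Suppose only the 3-hour sample is late, by 1 h. The interval labelled 0–3 then spans 4 h and the one labelled 3–6 spans 2 h. If it is 2 h late, they span 5 h and 1 h. If it is 3 h late, the whole 3-to-6-hour change already lies inside the sample labelled 3 hours. The problem is therefore concentrated at 3, 6 and 12 hours.

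For the value itself, assume an abnormality that resolves with half-time h. A sample drawn d hours late shows a fraction 2^(−d/h) of what a correct model gives at the nominal hour:

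- h = 12, d = 1: 0.944, a 6% shortfall
- h = 12, d = 3: 0.841, a 16% shortfall
- h = 6, d = 1: 0.891, an 11% shortfall
- h = 6, d = 3: 0.707, a 29% shortfall

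These are errors in a single late sample. Half-time, delay and steady recovery are all assumptions.

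**3. Can a group-level bias be derived?**

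Take 300 planned subjects and the protocol's statement that roughly 30% of trauma alerts lack significant injury: 0.30 × 300 = 90 against 210. Assume identical true time courses, a mean delay that differs by d hours, a marker that changes by s SD per hour, and a two-sided normal test at 5%. The spurious difference is s × d SD, with SE = √(1/90 + 1/210) = 0.126 SD.

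| s (SD/h) | d (h) | s × d (SD) | Rejection rate with no true difference |
|---|---|---|---|
| 0.05 | 0.5 | 0.025 | 5.5% |
| 0.05 | 1 | 0.05 | 6.8% |
| 0.1 | 1 | 0.1 | 12.5% |
| 0.1 | 2 | 0.2 | 35.5% |
| 0.2 | 2 | 0.4 | 88.8% |

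The result runs from negligible to severe according to two inputs, s and d, that the documents do not supply. Fewer samples per time point would lower the rates. The table shows that the size is undetermined; it does not estimate it.

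**The case against.** The schedule in Procedures is fixed. The sentence in Potential Study Risks minimises risk: it is best-effort and allows existing lines, from which a draw can be on time. Naming scheduled hours is ordinary protocol practice, a model integrated in time can be evaluated at any hour, and nothing forbids actual times. All of this is fair. What stands is that delay in unstable patients is explicit and unlimited, and that a plan followed as written has only nominal hours to work with. The continuous clinical files do not close the gap, because no section extends their timing to research assays.

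Three stronger readings are tempting, and the documents do not support them:

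- **Minimally injured patients are sampled late because they wait for routine draws.** This is inference; no section says so. If it were true, lateness would occur at both ends of the severity range and the net direction would be unclear.
- **The planned group comparisons are biased by a known amount.** The t-tests, Mann-Whitney tests and logistic regression in the Analysis Plan name no time point, so a 3-hour group contrast is not a specified analysis. The delay rule also covers only those unstable patients in whom the team judges that sampling would interfere, so a group-average delay would be diluted.
- **Every deferred sample is a mistimed one.** Deferred may mean never collected, which is a missing-data problem.

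The scope is also limited. An admission sample drawn with the clinical bloods is on time. The ROC comparison of microfluidic with standard coagulation measures is helped if both come from one draw. Urine is not shown to enter the model check.

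**Conclusion.** The concern holds for the model check and for any time-course analysis of post-admission samples. The documents permit unlimited delay in unstable patients, express the outcome and the model comparison only at nominal hours, and do not provide for recording or using actual draw times. The mismatch is most serious over the first 12 hours, where a 1-hour delay is 33% of a 3-hour gap and 17% of the 6-hour gap.

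Those percentages need only the schedule and an assumed delay. The 6–29% shortfall in a late sample needs an assumed half-time as well. The net bias between outcome groups, in direction and in size, cannot be derived. The change is still worth making: it is cheap, it gives a better comparison than nominal hours whatever the delays prove to be, and without recorded times the sponsor could not show that the error was negligible.

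**What to change.** 1. Record the clock time of every research blood and urine draw on the tube log or case report form.
2. Convert it to elapsed hours since admission before files go to the modelling collaborators. They receive de-identified data only, and the Data Protection section lists date elements among the identifiers.
3. State in the Analysis Plan that the model is integrated to each sample's actual elapsed time when it is compared with measurements.
4. Use actual elapsed time in any analysis of post-admission samples that models time. Keep nominal labels for display, and do not reassign a late sample to another scheduled hour: that could leave two samples at 6 hours and none at 3 hours, selectively in unstable patients.
5. Treat samples never collected as missing, separately from late ones.
6. Report the distribution of delay from nominal time by severity group.

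The cost is one extra time field, a short addition to the Analysis Plan and slightly more complex code. The sampling schedule and the clinical deferral rule are unchanged.
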